4.6.1.2 Presentation

The duration of exposure and exposure as measured by amount administered will be summarized using descriptive statistics according to the group defined in Section 4.6.1.1. Duration of exposure will also be presented categorically by using the cumulative categories as described above. Exposure over time will be presented in a figure, with one line for each treatment group.

A listing with individual exposure to study treatment will be presented.

4.6.2 Adverse Events

4.6.2.1 Definitions and Derivations

The Medical Dictionary for Regulatory Activities (MedDRA) (latest version) is used to code the AEs. AEs are graded according to their intensity (Mild, Moderate, Severe) and they will be classified by MedDRA system organ class (SOC) and MedDRA preferred term (PT).

For rules on missing or partial dates, see Section 3.3.1. AEs with a missing start time (or where time is not collected) which occur on the same day as first study treatment administration are reported as on-treatment.

The following definitions and principles are to be followed:

Any AE

Defined as participants with at least one reported AE with an onset date within the analysis periods defined in Section 3.3.1.3.

AEs with Outcome Death

Defined as an AE with reported outcome as ‘Fatal’, there may be more than one AE with outcome death for a participant. The start date of the AE determines the analysis period, irrespective of date of death.

AEs Leading to Discontinuation of study treatment

Defined as an AE with action taken study treatment reported as drug withdrawn. The start date of the AE determines the analysis period, irrespective of date of discontinuation of study treatment.

AEs Leading to Interruption of study treatment

Defined as an AE with action taken study treatment reported as drug interrupted. The start date of the AE determines the analysis period, irrespective of date of interruption of study treatment.

AEs Leading to Withdrawal of the Participant from the Study

Defined as an AE with action taken as Participant Withdrawn from Study. The onset date of the AE determines the analysis period, irrespective of date of withdrawal.

SAEs

Defined as participants with at least one reported serious AE, irrespective of outcome, with an onset date within the defined analysis period. The onset date of the premeditating AE determines whether the SAE belongs to the analysis period, irrespective of the date the AE becomes serious.

AEs Possibly Related to study treatment

Defined as an AE that is reported as “reasonable possibility of a causal relationship between the study treatment and the AE”. If this causality evaluation is missing, it will be counted as an AE possibly related to study treatment.

4.6.2.2 Presentation

Treatment groups will be presented according to [Table 2](#).

AEs are counted once for each participant for calculating percentages of participants experiencing AE. In addition, if the same AE occurs multiple times within a particular participant, the highest intensity and level of relationship observed are reported. For tables by MedDRA SOC and MedDRA PT, participants with multiple AEs are counted once for each SOC/PT.

The durations reported in the listings, will be derived only for fully completed dates as below:

- Time from first dose of study treatment to AE (in days) will be calculated as the AE start date minus date of first dose of study treatment +1. Time from first dose to death and AE becoming serious will be calculated with the corresponding formula.
- Time from (last dose prior to AE start) and (last dose prior to death) will be calculated as the (date of death or AE start date) minus the (date of last dose of study treatment prior to AE) and death, respectively, +1.

The following summary table will be presented on participant-level:

- Number of participants with any AE
- Number of participants with any AE considered related to study treatment
- Number of participants with any SAE with outcome of death
- Number of participants with any SAE
- Number of participants with any AE leading to discontinuation of study treatment
- Number of participants with any AE leading to interruption of study treatment
- Number of participants with any AE leading to withdrawal of participant from the study

The following summary tables will be presented by SOC and PT on participant-level:

- AEs
- AEs that are possibly related to study treatment
- SAEs
- SAEs with outcome of death
- SAEs that are possibly related to study treatment
- AEs leading to discontinuation of study treatment
- AEs by maximum intensity on the preferred term level.

The following summary tables will be presented by PT:

- AEs sorted by decreasing frequency of PT, based on the actual treatment arm “AZD0780 30 mg”

A list of key participant information for participants with SAEs with outcome of death, participants with SAEs, participants with AEs leading to discontinuation of study treatment will be provided. A listing of all AEs will also be provided.

A table with non-serious adverse events occurring in more than 5% of participants will be reported.

4.6.3 Clinical Laboratory, Blood Sample

4.6.3.1 Definitions and Derivations

Table 9 – Blood Sample Safety Variables

Haematology/Haemostasis	Clinical Chemistry

• Blood
○ Haematocrit○ Hb (g/L)○ Leukocyte count○ Leukocyte differential count (absolute count)○ MCV (fL)○ MCH (pg)○ MCHC (g/L)○ Platelet count○ RBC○ Reticulocyte absolute count○ Coagulation○ HbA1C	
• Plasma/Serum
○ Albumin (g/L)○ ALP (ukat/L)○ ALT (ukat/L)○ AST (μmol/L)○ Bilirubin, total (μmol/L)○ Bicarbonate (mmol/L)○ Blood urea nitrogen○ Creatinine (μmol/L)○ GGT (ukat/L)○ High sensitivity CRP (mg/L)○ Potassium (mmol/L)○ Sodium (mmol/L)○ Total Protein (g/L)• eGFR (mL/min/1.73m²)

ALP = alkaline phosphatase; ALT = alanine aminotransferase/transaminase; AST = aspartate aminotransferase/transaminase; CRP = C-reactive protein; eGFR: Glomerular Filtration Rate; GGT = gamma glutamyl transpeptidase; Hb = haemoglobin; MCH = mean corpuscular haemoglobin; MCHC = mean corpuscular haemoglobin concentration; MCV = mean corpuscular volume; RBC = red blood cell.

LLOQ and ULOQ

Laboratory parameters below the lower limit of quantification (LLOQ) for which the exact value cannot be determined, will be replaced with the LLOQ/sqrt(2) value. Similarly, laboratory test results above the upper limit of quantification (ULOQ) for which the exact value cannot be determined, will be replaced with the ULOQ value. After the LLOQ/ULOQ replacement, change from baseline to each post-baseline visit is defined as the post-baseline visit value minus the baseline value. After the LLOQ/ULOQ replacement, safety clinical laboratory results are also classified as normal (if value is within normal reference range), low (if value is below the normal reference range), and high (if value is above the normal reference range) based on the reference range indicator. Tables will utilize the LLOQ/ULOQ replacement. However, listings will display the original LLOQ/ULOQ inequality (e.g., “ $< x$ ” and “ $> x$ ”).

Abnormalities in Laboratory Parameters

Treatment emergent abnormalities are defined as abnormalities that manifested after the first administration of study treatment.

The predefined criteria for a parameter abnormality are based on reference ranges from the central lab and defined as $>\text{ULN}$ or $<\text{LLN}$, where applicable. In addition, the following definitions of abnormalities (non-mutually exclusive) will be used for specific parameters listed below:

- Platelet count: < 50 , < 75 , < 100 , $< 150 \times 10^9/\text{L}$, and $> 30\%$ decrease from baseline
- ALT: $> 1 \times \text{ULN}$, $> 3 \times \text{ULN}$, $> 5 \times \text{ULN}$, $> 10 \times \text{ULN}$, $> 20 \times \text{ULN}$
- AST: $> 1 \times \text{ULN}$, $> 3 \times \text{ULN}$, $> 5 \times \text{ULN}$, $> 10 \times \text{ULN}$, $> 20 \times \text{ULN}$
- ALP: $> 2 \times \text{ULN}$, $> 3 \times \text{ULN}$
- Total Bilirubin (TBL): $> 2 \times \text{ULN}$, $> 5 \times \text{ULN}$, $> 8 \times \text{ULN}$
- eGFR: $\geq 25\%$ decrease, $\geq 50\%$ decrease and $\geq 75\%$ decrease
- Creatinine: $\geq 1.5 \times \text{baseline}$, $\geq 2 \times \text{baseline}$ and $\geq 3 \times \text{baseline}$

Potential Hy's Law

Potential Hy's law is defined as AST or ALT $\geq 3 \times \text{ULN}$ together with TBL $\geq 2 \times \text{ULN}$ at any point during the study, following the start of study intervention irrespective of an increase in ALP. The elevation in transaminases must precede or be coincident with (i.e., on the same day) the elevation in TBL, but there is no specified timeframe within which the elevations in transaminases and TBL must occur.

Shift Tables

Shift tables will be presented for the following parameters according to unique thresholds:

For ALT and AST:

- $\leq 1 \times \text{ULN}$
- $> 1 \times \text{ULN}$ and $\leq 3 \times \text{ULN}$
- $> 3 \times \text{ULN}$ and $\leq 5 \times \text{ULN}$
- $> 5 \times \text{ULN}$ and $\leq 10 \times \text{ULN}$
- $> 10 \times \text{ULN}$ and $\leq 20 \times \text{ULN}$
- $> 20 \times \text{ULN}$

Bilirubin, total will be categorised into:

- $\leq 2 \times \text{ULN}$
- $> 2 \times \text{ULN}$ and $\leq 5 \times \text{ULN}$
- $> 5 \times \text{ULN}$ and $\leq 8 \times \text{ULN}$
- $> 8 \times \text{ULN}$

ALP will be categorised into:

- $\leq 2 \times \text{ULN}$
- $> 2 \times \text{ULN}$ and $\leq 3 \times \text{ULN}$
- $> 3 \times \text{ULN}$

Platelet absolute count will be categorised into:

- $< 50 \times 10^9/\text{L}$
- $\geq 50 \times 10^9/\text{L}$ and $< 75 \times 10^9/\text{L}$
- $\geq 75 \times 10^9/\text{L}$ and $< 100 \times 10^9/\text{L}$
- $\geq 100 \times 10^9/\text{L}$ and $< 150 \times 10^9/\text{L}$
- $\geq 150 \times 10^9/\text{L}$

Categories for parameters that are not listed above will be defined according to the mutually exclusive thresholds based on central laboratory ranges (when applicable):

- $< \text{LLN}$
- $\geq \text{LLN}$ and $\leq \text{ULN}$
- $> \text{ULN}$

Risk differences between active treatment groups and Placebo and 95% confidence intervals of the risk difference will be calculated according to the following formulas:

$$\delta_{\text{Trt-Placebo}} = \pi_{\text{Trt}} - \pi_{\text{Placebo}}$$

$$\text{Var}(\delta_{\text{Trt-Placebo}}) = \text{Var}(\pi_{\text{Trt}}) + \text{Var}(\pi_{\text{Placebo}})$$

$$CL_{\text{Trt-Placebo}}: \delta_{\text{Trt-Placebo}} \pm 1.96 * \sqrt{\text{Var}(\delta_{\text{Trt-Placebo}})}$$

Where:

- Trt: All strength of AZD0780 as presented in [Table 2](#) and AZD0780 Total
- $\delta_{\text{Trt-Placebo}}$ – Difference between treatment group and Placebo
- π – Proportion of subjects with given blood abnormalities in each treatment group
- $\text{Var}()$ – Variance of a given parameter
- CL – 95% confidence limits

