## **6.3 Assignment to Study Intervention**

All participants will be centrally assigned to randomized study intervention using an IRT/RTSM. The participant numbers will be obtained during screening for all participants, after the signature of the ICF, while the randomization codes will be assigned only to the participants proceeding to the treatment phase of the study. Before the study is initiated, the telephone number and call-in directions for the IRT and/or the log in information and directions for the RTSM will be provided to each site in the IRT/RTSM user manual.

In case of rescreening, the rescreened participants should be assigned the same participant number as for the initial screening.

Participants will be randomized to once daily dosing of placebo or different dose levels of AZD0780. Dosing should be supervised and documented by study staff when study intervention is administered in the clinic. Eligible participants will be randomized across 5 different treatment arms (approximately 75 participants in each arm) in a 1:1:1:1:1 ratio for a

12-week treatment period. The planned treatments arms are AZD0780 [redacted] mg, AZD0780 [redacted] mg, AZD0780 [redacted] mg, AZD0780 [redacted] mg, and placebo. A minimum of 5 participants and a maximum of 10 participants in each arm (a minimum of 25 in total and a maximum of 50 in total) will be allocated to sites in Japan. Separate randomization lists will be generated for Japan and for the rest of the world.

Investigational medicinal product will be available as film-coated oral tablets in labeled bottles containing either AZD0780 tablets or placebo tablets (35 tablets in a bottle).

Returned study intervention should not be re-dispensed to participants.

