#### **9.4.3 Safety**

Safety data will be summarized descriptively and will not be formally tested.

Safety data will be presented in the data listings.

Adverse events will be summarized by PT and SOC using MedDRA vocabulary.

Furthermore, listings of SAEs and AEs that led to withdrawal will be made and the number of participants who had any AE, SAEs, AEs that led to withdrawal, and AEs with severe intensity will be summarized.

Tabulations and listings of data for vital signs, clinical laboratory tests be presented. Results from safety ECGs will only be listed. Any new or aggravated clinically relevant abnormal

medical physical examination finding compared to the baseline assessment will be reported as an AE.

Out-of-range values for safety laboratory will be flagged in individual listings as well as summarized descriptively.

Safety analyses will be performed using the safety analysis set unless otherwise specified. Details of safety analyses will be provided in the SAP.

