4.6.3.2 Presentations

All laboratory data will be presented for the on-treatment and on-study periods using international system of units and presented as detailed in [Table 2](#).

Clinical laboratory parameters will be presented by scheduled visit, separately for haematology and chemistry parameters. All parameters will be presented as continuous variables with descriptive statistics for all visits at which an assessment is scheduled. Observed value, absolute change from baseline will be presented using descriptive statistics for all scheduled assessments after baseline.

The number of participants with treatment-emergent laboratory parameter abnormalities will be presented categorically in frequency tables, according to the categories defined in Section [4.6.3.1](#). Risk differences between active treatment groups and Placebo will be presented with 95% CI.

Key subject information will be separately listed for participants with haematology abnormalities, chemistry abnormalities, or potential Hy's law. Additionally, individual chemistry laboratory measurements and individual haematology laboratory measurements will be listed.

Shift tables from baseline to maximum on-treatment and on-study value, and from baseline to minimum on-treatment and on-study value will be presented by treatment group according to the categories defined in Section [4.6.3.1](#).

A descriptive table for maximum ALT and AST versus maximum total bilirubin for the on-treatment and on-study analysis periods will be shown.

Out-of-range values for safety laboratory will be flagged in individual listings as well as summarized descriptively.

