4.6.5.2 Presentations

Observed values and change from baseline in vital signs will be summarised by the treatment group and visit with descriptive statistics.

A figure with mean change from baseline over time by treatment group will be presented.

Shift tables from baseline to maximum on-treatment and on-study value (excluding Oxygen Saturation, because shift to maximum is not relevant), from baseline to minimum on-treatment and on-study value will be presented for each treatment group and AZD0780 Total.

Treatment emergent vital signs abnormalities will be reported as defined in Section 4.6.5.1.

Risk differences between active treatment groups and Placebo will be presented, alongside 95% confidence intervals of the risk difference according to the definitions in Section 4.6.3.1.

The key subject information about the treatment emergent vital signs abnormalities will also be listed. Additionally, individual vital signs data will be listed.

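### The SAP's ±1.96 SE limits for safety risk differences collapse to (0, 0) when neither group has an event, and are too narrow for AZD0780 Total against placebo when placebo has none

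*SAP*

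**What the plan says.** SAP 4.6.3.1 introduces the method with "Risk differences between active treatment groups and Placebo and 95% confidence intervals of the risk difference will be calculated according to the following formulas". The limits are the difference in proportions plus or minus 1.96 times the square root of the sum of the two group variances. The variance term is described only as "Variance of a given parameter". The active side is defined by "Trt: All strength of AZD0780 as presented in" Table 2, and the same line adds AZD0780 Total, so the pooled comparison uses the same limits.

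The rows come from the abnormality categories in the same section, where "the following definitions of abnormalities (non-mutually exclusive) will be used for specific parameters listed below". They include ALT and AST above 10 and 20 times ULN, total bilirubin above 8 times ULN, platelets below 50 × 10⁹/L and creatinine at least 3 times baseline.

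SAP 4.6.3.2 commits to printing the result: "Risk differences between active treatment groups and Placebo will be presented with 95% CI". Urinalysis (4.6.4.2) and vital signs (4.6.5.2) show risk differences "alongside 95% confidence intervals of the risk difference according to the definitions in Section 4.6.3.1". No section gives a zero-count rule, a continuity correction or another interval method. Protocol 6.3 plans "approximately 75 participants in each arm". Protocol 9.4.3 says: "Safety data will be summarized descriptively and will not be formally tested".

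**The concern.** A Wald interval estimates each group's variance from its own observed proportion. An observed proportion of zero gives a variance of zero, so a group with no events is treated as if its risk were known exactly. Many categories are rare and placebo has about 75 participants, so zero cells should be expected.

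Two kinds of row would mislead. With no events in either group, the table would claim complete certainty of no difference. In the AZD0780 Total column with no placebo events, the smaller group, which should dominate the uncertainty, would add none, and the interval could lie wholly above zero on a handful of events. The first is false reassurance and the second a false signal. Protocol 9.2 says safety and tolerability drive the sample size, so these tables matter.

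**Working it through.** **Inputs.** Multiplier 1.96 (SAP 4.6.3.1). About 75 per arm (Protocol 6.3; 375/5 = 75), so AZD0780 Total is 4 × 75 = 300. The safety analysis set is everyone randomised and dosed, so 75 is the relevant size rather than the 64 evaluable. *Assumption:* Var is p(1-p)/n; a divisor of n-1 also gives zero at p = 0. The documents state no event rates, so the coverage figures use assumed risks. The plan prints no risk difference or interval to reproduce.

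**Formulas.**
- SAP (Wald): d ± 1.96 √[p₁(1-p₁)/n₁ + p₀(1-p₀)/n₀].
- Newcombe: with Wilson limits (l, u) for each group, lower = d - √[(p₁-l₁)² + (u₀-p₀)²] and upper = d + √[(u₁-p₁)² + (p₀-l₀)²].
- The Wilson upper limit for 0/n is 3.8416/(n + 3.8416): 4.87% for n = 75 and 1.26% for n = 300.

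**Single tables (no risk assumed).**

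| Active v placebo | SAP formula | Newcombe |
|---|---|---|
| 0/75 v 0/75 | (0, 0) | (-4.9%, +4.9%) |
| 0/300 v 0/75 | (0, 0) | (-4.9%, +1.3%) |
| 4/300 v 0/75 | (+0.04%, +2.6%) | (-3.6%, +3.4%) |

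For 4/300 v 0/75, d = 1.333%. The SAP half-width is 1.96 × √(0.01333 × 0.98667/300) = 1.298%, so the lower limit is just above zero. The Wilson limits for 4/300 are 0.52% and 3.38%, so the Newcombe lower limit is 1.333 - √(0.813² + 4.873²) = -3.61%. Fisher's two-sided p for this table is 0.59.

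**When the interval first excludes zero, placebo 0/75.** With p₀ = 0 the SAP lower limit is positive when x > 3.8416 n₁/(n₁ + 3.8416). That is 3.79 for n₁ = 300 and 3.65 for n₁ = 75, so 4 events in either case; the placebo group's size has dropped out. For AZD0780 Total, Newcombe needs 16/300 and Miettinen-Nurminen 15/300. For a single dose the thresholds are 4/75 (SAP), 5/75 (Newcombe) and 4/75 (Miettinen-Nurminen), so little changes there.

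**Exact binomial enumeration, 300 v 75, equal true risks.**

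| True risk | SAP coverage | SAP lower limit > 0 | Newcombe coverage | Newcombe lower limit > 0 |
|---|---|---|---|---|
| 0.5% | 95.5% | 4.5% | 98% | 0% |
| 1% | 83% | 17% | 97% | 0% |
| 2% | 81% | 19% | 97% | 0% |
| 3% | 89% | 11% | 97% | 0.2% |
| 5% | 92% | 7% | 96% | 1.1% |

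The nominal one-sided error is 2.5%. At 1% and 2%, tables with no placebo event account for 16.6 of 16.6 and 18.7 of 18.8 percentage points of the false excesses. Placebo has no event in 47% of samples at 1% (0.99⁷⁵) and in 22% at 2%.

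**Where the formula does better.** At 75 v 75 with equal risks of 0.5%, 1% and 2%, it covers 99.9%, 99.3% and 96.9%. At 300 v 75 with unequal risks (1% v 0.5%, 2% v 0.5%, 2% v 1%), it covers 94%, 96% and 92%. At 75 v 75 with the same unequal pairs, coverage falls to 67%, 78% and 85%, mostly because 32%, 15% and 10% of samples have no event in either arm and print (0, 0).

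**The case against.** **Descriptive use.** Safety is not tested, counts stand beside the intervals, and a reader would recognise (0, 0) next to 0/75 v 0/75 as degenerate. This limits the harm and is why no study conclusion is at risk. It does not make a zero-width interval a 95% interval, and the lower limit of +0.04% for 4/300 v 0/75 does not look degenerate at all.

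**Assumed rates.** The one-in-six false excess arises only around 1-2%. At equal risks of 0.1%, 0.2% and 0.3%, the Total interval lies above zero in 0.02%, 0.3% and 1.1% of samples. If the most extreme categories are that rare, they will mainly show the (0, 0) problem or no problem. No listed category is tied to 1-2%. This stands as a limit on the coverage figures; the single-table results do not depend on it.

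**Newcombe has its own asymmetry.** At 300 v 75 with equal risks of 1%, 2% and 5%, its upper limit falls below zero in 2.6%, 3.3% and 3.2% of samples. With 0/300 on drug it excludes zero at 2/75 placebo events (-9.2%, -0.4%). It is also less sensitive: at true risks of 3% v 0.5%, its lower limit exceeds zero in 1.4% of samples against 68% for the SAP formula, which covers 95.3% there; at 5% v 0.5% the figures are 30% and 83%. All of this is true and should be known before choosing. The upper-side error stays close to 2.5%, and much of the apparent sensitivity comes from giving the placebo group no uncertainty, which also produces the false excesses.

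**Conclusion.** The concern holds. As written, the formula gives (0, 0) for every row with no events in either group, whatever the true risks. For AZD0780 Total against placebo with no placebo event, it excludes zero from 4/300. At assumed equal risks of 1-2%, the Total interval covers 79-83% (lowest 78.6%, at 1.5%) and shows a false excess on drug in 17-21% of samples. This rests on reading the variance as p(1-p)/n, on about 75 treated per arm and, for coverage only, on the assumed risks. With 64 per arm the pattern is the same: 4/256 v 0/64 gives (+0.04%, +3.1%) against Newcombe (-4.2%, +3.9%).

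The reach is limited. Single-dose comparisons at equal rare risks have no shortfall, common categories are little affected, AEs and ECG have no planned risk differences, and no efficacy result or formal test changes. It should be corrected because the limits are wrong as specified and the correction is cheap.

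**What to change.** In SAP 4.6.3.1, and so in 4.6.4.2 and 4.6.5.2, replace the formula with Newcombe (Wilson-based) limits for all rows, and say that they also apply when one or both groups have no events. Suppress no interval: 5/75 v 0/75 would be shown as (0.5%, 14.7%). The undefined variance term then disappears. Miettinen-Nurminen also removes the (0, 0) collapse, but at 300 v 75 it covers 91%, 94% and 96% at equal risks of 0.5%, 1% and 2%, so Newcombe is preferred.

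The cost is SAP wording and one procedure option. Intervals widen in rare-event rows; at 75 v 75 Newcombe is conservative (99.2-100% at equal risks of 0.5-2%). A real but rare excess in AZD0780 Total would be seen from the counts and listings before the interval excludes zero.

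A separate wording point that carries no weight here: SAP 4.6.1.1 describes exposure duration as days on study treatment, but its formula gives the length of the on-treatment period. A last dose on Day 74 counts as 74 + 10 = 84 days if the last visit is on or after Day 84. Keep the formula and relabel the result as length of the on-treatment period (last dose + 10 days, capped at the last study visit).
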